**Figure 1: Study Schematic**

During the treatment phase, participants will receive:

- Arm A: Nivolumab 480 mg IV Q4W for up to 52 weeks (12 months)
- Arm B: Nivolumab 480 mg IV Q4W for up to 52 weeks (12 months) and intravesical BCG (induction) weekly for 6 weeks followed by maintenance intravesical BCG weekly for 3 weeks at 3 months, 6 months and 12 months following the first intravesical dose. The dose used for each weekly intravesical treatment will be based on current prescribing information for the particular BCG strain and preparation administered. This may vary as BCG strain and/or preparation administered may vary based on geographic region in which the participant is receiving treatment. Every effort should be made to continue a participant on the same strain of BCG for the duration of study participation.
- Arm C: Nivolumab 480 mg IV Q4W and BMS-986205 100 mg PO QD for up to 52 weeks (12 months)
- Arm D: Nivolumab 480 mg IV Q4W and BMS-986205 100 mg PO QD for up to 52 weeks (12 months), and intravesical BCG (induction) weekly for 6 weeks followed by maintenance intravesical BCG weekly for 3 weeks at 3 months, 6 months, and 12 months following the first intravesical dose. The dose used for each weekly intravesical treatment will be based on current prescribing information for the particular BCG strain and preparation administered. This may vary as BCG strain and/or preparation administered may vary based on geographic region in which the participant is receiving treatment. Arm D enrollment will be paused after the safety lead-in.

For each arm, 1 treatment cycle equals 4 weeks.

Dose reductions are not permitted for nivolumab or for BCG after the safe-dose level has been determined in the safety lead-in. One dose reduction is permitted for BMS-986205, from 100 mg QD to 50 mg QD. No re-escalation is permitted after dose reduction.

Doses of nivolumab, BMS-986205 and BCG should be delayed due to treatment-related AEs described in Section 7.4 of the protocol. Treatment-related AEs resulting in permanent discontinuation of study treatment are described in Section 8 of the protocol. Treatment may be discontinued due to unacceptable toxicity, withdrawal of consent, disease recurrence or progression, or completion of treatment cycles and follow-up, whichever occurs first. An external Data Monitoring Committee (DMC) will provide independent oversight of safety and study conduct.

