### 7.1.1 Nivolumab Dosing

Participants should receive nivolumab at a dose of 480 mg as a 30-minute infusion on Day 1 of each treatment cycle (1 cycle = 4 weeks) until recurrence, progression, unacceptable toxicity, withdrawal of consent, or completion of 52 weeks of treatment, whichever occurs first. Participants randomized to Arms A or C should begin study treatment within 3 calendar days of randomization. Participants randomized to Arms B or D should begin study treatment within 3 calendar days of randomization or after 14 days from last TURBT or bladder biopsy, whichever is later.

No dose escalations or reductions are allowed for nivolumab after the safe-dose level has been determined in the safety lead-in. For Q4W dosing cycles, participants may be dosed within a  $\pm 3$  day window. Premedication is not recommended for the first dose of nivolumab.

Participants should be carefully monitored for infusion reactions during nivolumab administration. If an acute infusion reaction is noted, participants should be managed according to Section 7.7.5.

Doses of nivolumab may be interrupted (ie, infusion interruption), delayed, or discontinued depending on how well the participant tolerates the treatment. Dosing visits are not skipped, only delayed. BMS-986205 treatment should be continued if nivolumab dosing is interrupted or delayed. BMS-986205 treatment should be discontinued if nivolumab administration is discontinued.

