### 7.1.2 BMS-986205 Dosing

A bottle of BMS-986205 should be dispensed to participants at each Day 1 visit within a cycle. Participants should be instructed that BMS-986205 should be administered once a day

(approximately 24 hours apart) following a meal, with approximately 240 mL (8 oz.) of water. Refer to Pharmacy Manual for additional details on dosing administration. Full details regarding BMS-986205 formulation and mode of administration at the time of enrollment are detailed in the IB and pharmacy manual, which may be updated throughout the study. Please contact the Medical Monitor with any queries.

Participants should be provided with pill diaries at each visit and instructed to record intake of BMS-986205 in the diary after each daily administration.

BMS-986205 will be administered on an out-patient basis. On days when nivolumab is administered, the dose of BMS-986205 should be given before the dose of nivolumab.

Participants should receive BMS-986205 until recurrence, progression, unacceptable toxicity, withdrawal of consent by the participant, or completion of 12 months (52 weeks) of treatment, whichever occurs first. Participants randomized to Arms A or C should begin study treatment within 3 calendar days of randomization. Participants randomized to Arms B or D should begin study treatment within 3 calendar days of randomization or after 14 days from the last TURBT or bladder biopsy, whichever is later. Doses of BMS-986205 may be modified, delayed, or discontinued depending on how well the participant tolerates the treatment (See [Section 7.4.2](#) [modification], [Section 7.4.4.2](#) [delay], and [Section 8.1.2](#) [discontinuation]). If the dose of BMS-986205 is reduced, re-escalation will not be permitted. Skipped doses during dose delays should not be administered within the same cycle.

If nivolumab dosing is delayed for reasons other than study drug toxicity (eg, administrative issues, holidays, etc), BMS-986205 dosing should continue uninterrupted.

For details on prepared drug storage, preparation, and administration, please refer to the BMS-986205 IB and/or pharmacy binder. The selection and timing of dose for each participant is provided in [Table 7.1-1](#).

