#### **7.4.2 BMS-986205 Dose Modifications**

A dose reduction of BMS-986205 is defined as a change from a 100 mg QD tablet to a 50 mg QD tablet.

Only one dose reduction is permitted. The participant must discontinue study treatment if a subsequent dose reduction of BMS-986205 is required (see [Section 8.1.2](#)).

Re-escalation of BMS-986205 will not be permitted once the dose of BMS-986205 has been reduced for a participant.

Doses of BMS-986205 should be reduced for the following AEs attributable to study therapy that do not otherwise meet criteria for discontinuation:

- Grade 3 fatigue, nausea, vomiting, or anemia related to study treatment
- Methemoglobin  $\geq 15\%$

- Clinically significant elevations in methemoglobin (generally 10%, with a normal hemoglobin level) with any associated Grade 3 AE (hypoxia, dyspnea, confusion, etc.) attributable to sustained elevations of methemoglobin and not attributable to another etiology
- QTcF > 500 msec confirmed by at least 1 repeat ECG and at least 60 msec above baseline (See [Appendix 8](#))

Dose modification and delay of BMS-986205 may occur in the setting of lower grade AEs and/or be more conservative than indicated above based on the clinical judgment of the investigator and in consultation with the BMS Medical Monitor/designee. For an AE requiring dose modification, BMS-986205 should be delayed to allow improvement of the AE, even if the AE does not otherwise meet criteria for dose delay (Section 7.4.4.2).

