#### **7.4.4.2 Nivolumab Plus BMS-986205**

Nivolumab and BMS-986205 administration should be delayed for the following:

- Grade 2 non-skin, drug-related AE, with the exception of fatigue, nausea, vomiting and anemia

- Grade 2 drug-related creatinine, AST, ALT and/or Total Bilirubin abnormalities
- Grade 3 skin, drug-related AE
- Grade 3 drug-related fatigue, nausea, vomiting, and anemia
- Grade 3 drug-related laboratory abnormality, with the following exceptions:
  - Grade 3 lymphopenia or asymptomatic amylase or lipase elevations do not require dose delay
  - Grade  $\geq 3$  AST, ALT, or Total Bilirubin will require dose discontinuation (see [Section 8.1](#))
- SARS-CoV-2 infection, either confirmed or suspected
- Any AE, laboratory abnormality, or intercurrent illness which, in the judgment of the investigator, warrants delaying the dose of study medication

If nivolumab dosing is delayed for reasons other than study drug toxicity (eg, administrative issues, holidays, etc.), BMS-986205 dosing should continue uninterrupted.

In addition, **only BMS-986205** should be delayed for the following:

- Methemoglobin  $\geq 15\%$
- Clinically significant elevations in methemoglobin (generally 10% with a normal hemoglobin level) with any associated Grade 3 AE (hypoxia, dyspnea, confusion, etc.) attributable to sustained elevations of methemoglobin and not attributable to another etiology
- QTcF  $> 500$  msec confirmed by at least 1 repeat ECG and at least 60 msec above baseline (See [Appendix 8](#))

Participants may continue to receive nivolumab during dose delays of BMS-986205 for elevations of methemoglobin and associated events, as well as QTcF prolongations.

For participants with methemoglobin elevations with associated Grade 3 AEs, if a contribution of nivolumab to the associated AE cannot be ruled out (eg, a participant with dyspnea in whom pneumonitis has not yet been ruled out), nivolumab dosing should be delayed as well. See [Section 7.7.4](#) for management of methemoglobinemia.

If BMS-986205 dosing is delayed, dose reduction may be necessary. See [Section 7.4.2](#).

If dosing is resumed after a delay, BMS-986205 may be resumed as soon as the criteria to resume treatment are met (see [Section 7.4.5.2](#)). Nivolumab should be resumed as soon as possible after criteria to resume treatment are met but may be resumed later than BMS-986205 given the differences in each drug's administration.

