**Table 7.4.4.2-1: Summary Table for Dose Delay and Reduction**

Situation	Nivolumab delay	BMS-986205 delay	BMS-986205 Reduction after Delay
Grade 2 non-skin, drug-related AE, except fatigue, nausea, vomiting and anemia	Yes	Yes	No
Grade 2 drug-related creatinine, AST, ALT and/or Total Bilirubin abnormalities	Yes	Yes	No
Grade 3 skin, drug-related AE	Yes	Yes	No
Grade 3 drug-related laboratory abnormality (exceptions apply)	Yes	Yes	No
Grade 3 drug-related fatigue, nausea, vomiting, and anemia	Yes	Yes	Yes
Methemoglobin $\geq$ 15% or any clinically significant elevation with associated Gr 3 AE not attributable to another etiology	No	Yes	Yes
QTcF > 500 msec (and > 60 msec above baseline)	No	Yes	Yes
Other lower grade AEs (in consultation with Medical Monitor/designee)	Possibly Yes	Possibly Yes	Possibly Yes

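### Section 7.1.1 continues BMS-986205 through any nivolumab delay, with no toxicity exception, and so contradicts the joint hold in Section 7.4.4.2 for toxicity delays

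*Combined protocol and SAP*

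**What the plan says.** **Section 7.1.1 (Nivolumab Dosing)** allows nivolumab to be interrupted (meaning an interrupted infusion), delayed or stopped, depending on tolerance. It then says: "BMS-986205 treatment should be continued if nivolumab dosing is interrupted or delayed". BMS-986205 is stopped if nivolumab is stopped. The only section it refers to is 7.7.5, on infusion reactions.

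**Section 7.4.4.2 (Nivolumab Plus BMS-986205)** opens its list with "Nivolumab and BMS-986205 administration should be delayed for the following" and gives seven triggers. After the list it adds: "If nivolumab dosing is delayed for reasons other than study drug toxicity (eg, administrative issues, holidays, etc.), BMS-986205 dosing should continue uninterrupted". It then names events that hold BMS-986205 alone: raised methemoglobin and QTcF prolongation.

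**Table 7.4.4.2-1** summarises delay and reduction for both drugs in Arms C and D. Its first row is "Grade 2 non-skin, drug-related AE, except fatigue, nausea, vomiting and anemia", with delay marked Yes for both drugs.

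**Section 7.1.2 (BMS-986205 Dosing)** repeats the limit, beginning "If nivolumab dosing is delayed for reasons other than study drug toxicity", and sends the reader to 7.4.4.2 for delays.

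**Section 7.4.2 (BMS-986205 Dose Modifications)** says: "For an AE requiring dose modification, BMS-986205 should be delayed to allow improvement of the AE". This applies even where no delay criterion is otherwise met.

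**The synopsis (Treatment Arms and Duration)** says: "Doses of nivolumab, BMS-986205 and BCG should be delayed due to treatment-related AEs described in Section 7.4 of the protocol".

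**The concern.** In Arms C and D a site can find two instructions for the same event. If nivolumab is delayed for, say, a drug-related Grade 2 transaminase elevation, 7.1.1 says to keep giving BMS-986205 and 7.4.4.2 says to hold it. The 7.1.1 sentence cannot comfortably be read as covering administrative delays only, because it comes shortly after a sentence about tolerability.

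This is a dosing rule that protects participants. BMS-986205 is taken daily, and Section 9.5.1 reports 2.1- to 3.6-fold accumulation between Days 1 and 14. Section 3.3 calls clinical experience with it limited. That section lists fatigue, nausea and transaminase elevations among its commonest drug-related events, and reports drug-related Grade 3 anemia in about 1.4% of participants. These are the kinds of event for which 7.4.4.2 holds both drugs once the stated grade is reached. Safety is also the main objective left after Protocol Amendment 04, so uneven holding across sites would blur the data still being collected.

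**Working it through.** No calculation applies beyond a count, so the texts are set side by side.

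**Step 1. Table 7.4.4.2-1 against the 7.1.1 sentence, taken literally.**

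| Row | Situation (abridged) | Nivolumab delay | BMS-986205 delay | Conflict with 7.1.1? |
|---|---|---|---|---|
| 1 | Grade 2 non-skin AE, with exceptions | Yes | Yes | Yes |
| 2 | Grade 2 creatinine, AST, ALT or bilirubin | Yes | Yes | Yes |
| 3 | Grade 3 skin AE | Yes | Yes | Yes |
| 4 | Grade 3 laboratory abnormality, with exceptions | Yes | Yes | Yes |
| 5 | Grade 3 fatigue, nausea, vomiting, anemia | Yes | Yes | Yes |
| 6 | Methemoglobin | No | Yes | No: nivolumab not delayed |
| 7 | QTcF | No | Yes | No: nivolumab not delayed |
| 8 | Other lower-grade AEs | Possibly | Possibly | No fixed rule |

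Count: 5 + 2 + 1 = 8 rows, of which 5 conflict. No row delays nivolumab for toxicity while continuing BMS-986205.

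**Step 2. The list in 7.4.4.2.** It has seven triggers. Five correspond to rows 1 to 5. The other two, SARS-CoV-2 infection and the investigator-judged event, are not separate table rows (5 + 2 = 7).

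**Step 3. Which part of the 7.1.1 sentence is wrong.**

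- *Infusion interrupted:* nothing in 7.4.4.2 or the table stops BMS-986205 for this. No conflict.
- *Nivolumab delayed for administrative reasons:* 7.1.1, 7.1.2 and 7.4.4.2 all continue BMS-986205. No conflict.
- *Nivolumab delayed for toxicity:* 7.1.1 continues it; 7.4.4.2 and rows 1 to 5 hold it. Conflict.

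**Step 4. Does any text set an order of precedence?** Section 3.1.2 says that changes made by Protocol Amendment 04 override conflicting requirements. For 7.4.4.2 the amendment's summary of key changes lists only the SARS-CoV-2 addition. The clause therefore settles that trigger and leaves the five toxicity rows untouched. The synopsis and 7.1.2 point to Section 7.4, but neither withdraws the 7.1.1 instruction.

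**Step 5. Is the missing exception used elsewhere?** Yes. Section 7.1.3 lets the other drugs continue when BCG is delayed, and BCG continue when they are delayed. In each direction it makes an exception for toxicity that meets the delay criteria of the drug being continued. Section 7.1.1 has no such exception.

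**The case against.** The best defence is that the protocol answers the question elsewhere. Section 7.1.1 is the nivolumab section. BMS-986205 dosing is set out in 7.1.2, which follows at once, carries the non-toxicity limit and points to 7.4.4.2. The synopsis sends delays of all three drugs to Section 7.4. Moreover, 7.1.1 contains no delay criteria, so a site deciding to delay nivolumab for toxicity must open Section 7.4.4, where the list for the combination names both drugs in its first line. Most of this stands, and it is why the point is minor. It does not remove the contradiction: a flat instruction remains, and sites must infer that it does not mean what it says.

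Three stronger readings are tempting and should not be adopted.

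- *That the whole 7.1.1 sentence is wrong.* It is not: infusion interruptions and administrative delays are handled consistently (Step 3).
- *That 7.4.2 is a further conflict.* The overlap, Grade 3 fatigue, nausea, vomiting or anemia, is row 5, which is already counted.
- *That the non-toxicity limit in 7.1.2 and 7.4.4.2 clashes with the list item "Any AE, laboratory abnormality, or intercurrent illness which, in the judgment of the investigator, warrants delaying the dose of study medication".* Literally, an unrelated illness is not drug toxicity. But the examples beside the limit are administrative, and the list item applies only once the investigator has judged that a delay is warranted. Rewording the limit would be a drafting preference.

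**Conclusion.** The point holds for toxicity delays in Arms C and D: one sentence in 7.1.1 contradicts 7.4.4.2 and 5 of the 8 rows of Table 7.4.4.2-1, and omits the limit that 7.1.2 and 7.4.4.2 carry. It is a minor inconsistency of wording in a safety rule. No sample size, error rate or analysis changes.

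The judgment that the practical effect is small assumes that investigators follow the pointers to Section 7.4. Exposure is also shrinking, because enrollment closed on 02-Jun-2021 and treatment is capped at 52 weeks. Under Section 3.1.2, however, participants on treatment could continue and consented participants in screening could still be randomized.

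A reader might infer that participants were dosed through required holds. The documents do not show this. They give neither the number of Arm C and D participants still on treatment nor the length of a typical hold, so no count of affected doses or participants is made.

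**What to change.** Replace the sentence in 7.1.1 with wording such as: *Continue BMS-986205 through a nivolumab infusion interruption or a nivolumab delay, unless the participant meets any BMS-986205 dose delay criterion (Section 7.4.4.2) or requires a BMS-986205 hold under Section 7.4.2.* This follows the pattern of 7.1.3.

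The exception should cover any BMS-986205 criterion, and not only those that hold both drugs. With the narrower wording, a participant whose nivolumab is late for an administrative reason and whose methemoglobin is 15% or higher would literally continue BMS-986205. The reference to 7.4.2 is needed because that hold applies even where no delay criterion is met.

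No change to 7.1.2, 7.4.4.2 or the table is needed. The cost is one clause, issued by clarification letter or with the next amendment, with no new data, visits or analyses.

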### 7.1.2 BMS-986205 Dosing

A bottle of BMS-986205 should be dispensed to participants at each Day 1 visit within a cycle. Participants should be instructed that BMS-986205 should be administered once a day

(approximately 24 hours apart) following a meal, with approximately 240 mL (8 oz.) of water. Refer to Pharmacy Manual for additional details on dosing administration. Full details regarding BMS-986205 formulation and mode of administration at the time of enrollment are detailed in the IB and pharmacy manual, which may be updated throughout the study. Please contact the Medical Monitor with any queries.

Participants should be provided with pill diaries at each visit and instructed to record intake of BMS-986205 in the diary after each daily administration.

BMS-986205 will be administered on an out-patient basis. On days when nivolumab is administered, the dose of BMS-986205 should be given before the dose of nivolumab.

Participants should receive BMS-986205 until recurrence, progression, unacceptable toxicity, withdrawal of consent by the participant, or completion of 12 months (52 weeks) of treatment, whichever occurs first. Participants randomized to Arms A or C should begin study treatment within 3 calendar days of randomization. Participants randomized to Arms B or D should begin study treatment within 3 calendar days of randomization or after 14 days from the last TURBT or bladder biopsy, whichever is later. Doses of BMS-986205 may be modified, delayed, or discontinued depending on how well the participant tolerates the treatment (See [Section 7.4.2](#) [modification], [Section 7.4.4.2](#) [delay], and [Section 8.1.2](#) [discontinuation]). If the dose of BMS-986205 is reduced, re-escalation will not be permitted. Skipped doses during dose delays should not be administered within the same cycle.

If nivolumab dosing is delayed for reasons other than study drug toxicity (eg, administrative issues, holidays, etc), BMS-986205 dosing should continue uninterrupted.

For details on prepared drug storage, preparation, and administration, please refer to the BMS-986205 IB and/or pharmacy binder. The selection and timing of dose for each participant is provided in [Table 7.1-1](#).

### **7.1.3 BCG Dosing**

The first BCG treatment will begin a minimum of 14 days after the bladder biopsy and/or TURBT performed prior to randomization. Participants should receive an intravesical instillation of BCG weekly for 6 weeks starting on Day 1 of treatment, and then weekly for 3 weeks at 3 months, 6 months and 12 months after the first BCG dose. See [Table 2-3](#) for the BCG dosing schedule. BCG should not be given within 14 days after any TURBT or bladder biopsy.

No dose escalations or reductions are allowed for BCG after the safe-dose level has been determined in the safety lead-in.

The BCG dose should be prepared and administered according to the package insert. **BCG may be obtained by the investigational sites as local commercial product in certain countries if allowed by local regulations. These products should be prepared/stored/administered in accordance with the package insert or summary of product characteristics (SmPC).**

A urethral catheter will be inserted into the bladder by a qualified medical professional under aseptic conditions. The bladder will then be drained, after which the BCG suspension will be

instilled slowly, under gravity. The catheter will then be withdrawn. BCG should not be given if the urethra is traumatized during catheter insertion or if there is gross hematuria.

The participant should retain the BCG suspension for as long as possible for up to 2 hours. The participant should lie prone during the first 15 minutes following instillation, after which the participant is allowed to be in the upright position. At the end of 2 hours, the participant should void in the seated position. The participant will be instructed to maintain adequate fluid intake in the hours following BCG treatment to flush the bladder.

Participants should receive BCG until recurrence, progression, unacceptable toxicity, withdrawal of consent by the participant, or completion of 52 weeks of treatment, whichever occurs first. Participants should begin study treatment within 3 calendar days of randomization or 14 days after the last bladder tumor resection or bladder biopsy, whichever occurs later. If BCG treatment is delayed for any reason, nivolumab with or without BMS-986205 treatment should continue as scheduled, unless the participant has study drug toxicity meeting nivolumab and/or BMS-986205 dose delay criteria. If nivolumab and/or BMS-986205 treatment is delayed for any reason, BCG treatment should continue as scheduled, unless the participant has study drug toxicity meeting BCG dose delay criteria.

For details on prepared drug storage, preparation, and administration, please see the BCG package insert.

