## 2) Prior/Concomitant Therapy

- a) Participants with a condition requiring systemic treatment with either corticosteroids (> 10 mg daily prednisone equivalent) or other immunosuppressive medications within 14 days of start of study treatment. Inhaled or topical steroids, and adrenal replacement steroid doses > 10 mg daily prednisone equivalent, are permitted in the absence of active autoimmune disease.
- b) Prior treatment with an anti-PD-1, anti-PD-L1, anti-PD-L2, or anti-CTLA-4 antibody, or any other antibody or drug specifically targeting T-cell co-stimulation or checkpoint pathways
- c) Prior treatment with BMS-986205 or any other IDO1 inhibitors
- d) Treatment with botanical preparations (eg, herbal supplements or traditional Chinese medicines) intended for general health support or to treat the disease under study within 2 weeks prior to randomization
- e) Prior systemic chemotherapy or immunotherapy for UC. Intravesical chemotherapy and/or interferon administered prior to the date of tumor sample submission is permitted.
- f) Prior radiation therapy for bladder cancer
- g) Prior surgery for bladder cancer other than TURBT and/or bladder biopsies
- h) Use of an investigational agent within 4 weeks of randomization.
- i) Participants who have received a live /attenuated vaccine within 30 days of first treatment.

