**7.4.4.3 BCG**

Administration of BCG should be delayed if the participant develops a concurrent febrile illness, a urinary tract infection (UTI), or gross hematuria during the treatment period. Administration of nivolumab or nivolumab plus BMS-986205 should not be delayed if BCG treatment is delayed.

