#### **7.4.5.3 BCG**

BCG administration can resume when the concurrent febrile illness, UTI, or gross hematuria resolve and antibiotic treatment has ended.

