##### **7.7.1.1 Prohibited Treatments**

The following medications are prohibited during the study (unless utilized to treat a drug-related AE):

- Concomitant use of strong inhibitors of CYP3A4 and/or CYP1A2 or strong inducers of CYP3A4 and/or CYP1A2 (see [Appendix 7](#)) (Treatment Arm C and D only)
- Immunosuppressive agents

- Immunosuppressive doses of systemic corticosteroids (except as stated in [Sections 7.7.2 and 7.7.3](#))
- Any concurrent anti-neoplastic therapy (ie, chemotherapy, hormonal therapy, immunotherapy, extensive, non-palliative radiation therapy, or standard or investigational agents for treatment of malignancy)
- Any complementary medications (eg, herbal supplements or traditional Chinese medicines) intended to treat the disease under study. Such medications are permitted if they are used as supportive care. Please see [Section 7.7.1.2](#) for additional restricted medications. BMS Medical Monitor (or designee) approval is required prior to concurrent use with BMS-986205
- Prophylactic antimicrobial therapy except for those administered prior to TURBT as per the institutional guidelines
- Any live/attenuated vaccine (eg, varicella, zoster, yellow fever, rotavirus, oral polio, and measles, mumps, rubella [MMR]) during treatment and until 100 days post last dose.

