  - Grade 4 drug-related endocrinopathy AEs, such as, hyper- or hypothyroidism, or glucose intolerance, which resolve or are adequately controlled with physiologic hormone replacement (corticosteroids, thyroid hormones) or glucose-controlling agents, respectively, may not require discontinuation after discussion with and approval from the BMS Medical Monitor/designee.
- Any AE, laboratory abnormality, or intercurrent illness which, in the judgment of the investigator, presents a substantial clinical risk to the participant with continued nivolumab dosing
- Any event requiring 10 mg per day or greater prednisone or equivalent for more than 12 weeks
- Any event that leads to delay in dosing lasting > 10 weeks from the previous dose requires discontinuation, with the following exceptions:
  - Dosing delays to allow for prolonged steroid tapers to manage drug-related AEs are allowed. (Note: Protocol AE management algorithms provide guidance to initiate steroid

taper when AE has resolved to  $\leq$  Grade 1. Therefore, persistent Grade  $\geq$  2 AEs necessitating delay for  $>$  10 weeks would require discontinuation).

- Dosing delays lasting  $>$  10 weeks from the previous dose that occur for non-drug-related reasons may be allowed if approved by the BMS Medical Monitor/designee.

Prior to re-initiating treatment in a participant with a dosing delay lasting  $>$  10 weeks, the BMS Medical Monitor/designee must be consulted. Efficacy assessments must continue as per protocol even if dosing is delayed. Periodic study visits to assess safety and laboratory studies should also continue every 4 weeks or more frequently if clinically indicated during such dosing delays.

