## **APPENDIX 5            MANAGEMENT ALGORITHMS FOR STUDIES UNDER CTCAE VERSION 4.0**

These general guidelines constitute guidance to the Investigator and may be supplemented by discussions with the Medical Monitor representing the Sponsor. The guidance applies to all immuno-oncology agents and regimens.

A general principle is that differential diagnoses should be diligently evaluated according to standard medical practice. Non-inflammatory etiologies should be considered and appropriately treated.

[figure not shown]
Corticosteroids are a primary therapy for immuno-oncology drug-related adverse events. The oral equivalent of the recommended IV doses may be considered for ambulatory patients with low-grade toxicity. The lower bioavailability of oral corticosteroids should be taken into account when switching to the equivalent dose of oral corticosteroids.

Consultation with a medical or surgical specialist, especially prior to an invasive diagnostic or therapeutic procedure, is recommended.

The frequency and severity of the related adverse events covered by these algorithms will depend on the immuno-oncology agent or regimen being used.

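### Section 7.1.3 keeps live BCG on schedule while nivolumab is held, and the protocol body has no rule to hold BCG temporarily during systemic immunosuppression for a drug-related AE

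*Combined protocol and SAP*

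**What the plan says.** **Continuing BCG.** Section 7.1.3 covers the case where nivolumab and/or BMS-986205 is delayed, whatever the reason: "BCG treatment should continue as scheduled, unless the participant has study drug toxicity meeting BCG dose delay criteria". The same section requires BCG to be prepared and given according to its package insert.

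**Delaying and resuming BCG.** Section 7.4.4.3 gives the delay criteria: "Administration of BCG should be delayed if the participant develops a concurrent febrile illness, a urinary tract infection (UTI), or gross hematuria". Section 7.4.5.3 mirrors them: "BCG administration can resume when the concurrent febrile illness, UTI, or gross hematuria resolve and antibiotic treatment has ended".

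**Immunosuppression on study.** Section 7.7.1.1 bans immunosuppressive agents and immunosuppressive doses of systemic corticosteroids, with an exception in its opening line: "The following medications are prohibited during the study (unless utilized to treat a drug-related AE"). Appendix 5 makes that exception routine: "Corticosteroids are a primary therapy for immuno-oncology drug-related adverse events".

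**Holding nivolumab.** Section 8.1.1 ends nivolumab for delays beyond 10 weeks, but with an exception: "Dosing delays to allow for prolonged steroid tapers to manage drug-related AEs are allowed". It also ends nivolumab for "Any event requiring 10 mg per day or greater prednisone or equivalent for more than 12 weeks".

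**Stopping BCG.** Section 8.1.3 permanently stops BCG when nivolumab must be discontinued, when the investigator sees a substantial clinical risk in continuing it, or after a systemic BCG reaction or BCG infection.

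**The concern.** Read together, these sections allow a participant to spend weeks on immunosuppressive treatment with nivolumab held while a live organism remains due. At entry, exclusion criterion 2a of section 6.2 would have kept that person out: "Participants with a condition requiring systemic treatment with either corticosteroids (> 10 mg daily prednisone equivalent) or other immunosuppressive medications within 14 days" of starting treatment.

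Two contrasts suggest an omission rather than a decision. First, the delay lists for nivolumab (7.4.4.1) and for nivolumab plus BMS-986205 (7.4.4.2) each end with an investigator-judgement item, and the BCG list has none. Second, after Grade 2 hepatic abnormalities, 7.4.5.1 makes nivolumab wait until any steroid management is complete. BCG has no counterpart.

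The stake is participant safety. Section 5.1.1 counts disseminated BCG infection as a dose-limiting toxicity, and 3.2.4 names an intact immune system among the requirements for BCG to work. An instillation during immunosuppression may thus offer less benefit while a hazard that the protocol lists remains. Section 3.3 says the safety of nivolumab combined with BCG is not yet known. Amendment 04 lets treated participants continue, so 7.1.3 is still in force for them.

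**Working it through.** The plan states no figure on this point, so the main check is textual. A schedule count then shows how often the gap could matter.

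**1. The rules for one participant.** Take an Arm B participant with drug-related Grade 2 pneumonitis treated with systemic steroids.
- 7.4.4.1: Grade 2 non-skin drug-related AE, so nivolumab is delayed.
- 7.7.1.1: the steroids treat a drug-related AE, so they are allowed.
- 7.4.5.1: persistent Grade 1 pneumonitis after a taper of at least 1 month can still lead to retreatment, so nivolumab need not end.
- 8.1.3: nivolumab is not discontinued, so this trigger for stopping BCG is not met.
- 7.4.4.3: without fever, UTI or gross hematuria, no BCG delay criterion is met.
- 7.1.3: BCG stays due.

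Footnote b of Table 2-3 mentions nivolumab delay, but only to release the ±3-day alignment of BCG with nivolumab at C4D1, C7D1 and C13D1. It is not a hold.

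**2. Overlap with the BCG schedule.** Inputs:
- The 15 BCG visits in Table 2-3, footnote b. With 28-day cycles, day = 28 × (cycle − 1) + day in cycle, which gives days 1, 8, 15, 22, 29, 36, 85, 92, 99, 169, 176, 183, 337, 344 and 351.
- Duration of immunosuppression, L = 2, 4 or 12 weeks. These are assumptions. Twelve weeks is the longest course at 10 mg/day or more that 8.1.1 tolerates before nivolumab, and so BCG, must stop.
- Onset day s, assumed uniform over a stated range.

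Formula: share = (number of onset days s with at least one BCG day in [s, s + 7L)) ÷ (number of onset days).

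| Onset range | 2 weeks | 4 weeks | 12 weeks |
|---|---|---|---|
| Days 29–337 | 78/309 = 25.2% | 120/309 = 38.8% | 239/309 = 77.3% |
| Days 8–337 | 99/330 = 30.0% | 141/330 = 42.7% | 260/330 = 78.8% |
| Days 184–337 | 14/154 = 9.1% | 28/154 = 18.2% | 84/154 = 54.5% |

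The last row starts after the 6-month maintenance course, when only the three 12-month doses remain. It suits participants already well into treatment.

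**3. How many people.** The documents do not give the number treated with BCG. Assume 30 to 70 ever received it. Section 5.5.2 reports pneumonitis 2%, autoimmune hepatitis 1%, colitis 1% and uveitis 1% in a different study without BCG, so at most 2 + 1 + 1 + 1 = 5%.
- With such an AE: 30 × 5% = 1.5 to 70 × 5% = 3.5.
- Meeting an instillation: 1.5 × 25.2% = 0.4 to 3.5 × 77.3% = 2.7.

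This counts everyone ever treated. A change now reaches only those still on treatment, a smaller and unstated number with fewer doses left. AEs that end nivolumab lower the figure, and other steroid-treated AEs raise it.

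**The case against.** The strongest reply is that a site complying with 7.1.3 must also follow the BCG package insert, because 7.1.3 itself requires it. If the label restricts BCG under immunosuppression, the site has its rule. This stands as a limit: the insert is not in the documents and the Appendix 5 flowcharts are not reproduced, so the most that can be said is that the protocol body shows no such rule. If the label does restrict BCG, however, it conflicts with the instruction in 7.1.3 to continue as scheduled, and that also calls for clarification.

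Other safeguards exist. The synopsis says that doses, BCG included, are delayed for treatment-related AEs, but it points to section 7.4, whose BCG list is the one at issue. Section 8.1 stops treatment when the investigator judges that continuing is not in the participant's best interest. Section 9 requires immediate safety concerns to be discussed with the sponsor. Appendix 2 permits departures to remove an immediate hazard. Section 8.1.3 lets the investigator stop BCG. So a reader might infer that sites are bound to instil BCG against their judgement. The documents do not support that. These safeguards rest on case-by-case judgement, though, and 8.1.3 offers only permanent discontinuation. None of them is a temporary hold.

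A reader might also infer that the documents show steroids to raise the risk of BCG infection. They do not. The statement in 3.2.4 concerns efficacy, the dose-limiting toxicity list does not mention steroids, and criterion 2a applies to every arm, so it is not a BCG safety rule. The size of any added risk cannot be taken from the documents.

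**Conclusion.** The point holds as a gap in the dosing rules. Section 7.1.3 gives an explicit instruction to continue, its only stated exception leads to a list that omits immunosuppression and investigator judgement, and the visible safeguards do not supply a temporary hold. It is confined to AEs that delay nivolumab without ending it.

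Few people are affected: roughly 0.4 to 2.7 of those ever treated with BCG, under the assumed 30 to 70 treated, the borrowed 5% AE rate and assumed durations of 2 to 12 weeks. Fewer can still benefit from a change. Confidence is medium because the label and the flowcharts cannot be read. No estimate, endpoint or analysis is affected. The case for acting rests on the seriousness of the hazard and the small cost of the change, not on frequency.

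**What to change.** - **7.4.4.3, add:** Delay BCG while the participant receives immunosuppressive agents or systemic corticosteroids above 10 mg/day prednisone equivalent (other than physiologic adrenal replacement), or for any AE or intercurrent illness that in the investigator's judgement warrants delay.
- **7.4.5.3, add:** Resume when immunosuppressive agents have ended and the non-replacement steroid dose is 10 mg/day or less.
- **7.1.3:** cross-refer to both.

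The delay criterion is not limited to drug-related AEs, so it also covers the brief steroid courses permitted by 7.7.3 when they exceed the threshold. The 10 mg/day value is the protocol's own eligibility threshold (6.2 and 7.7.2), and the adrenal-replacement exception accompanies it there. It is not an established BCG safety limit, and the sponsor should confirm it against the BCG label.

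Cost: a minor amendment needing IRB/IEC approval, and health authority approval where applicable (Appendix 2), plus a few delayed instillations. Sample size and analyses stay as they are.
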